5. STUDY DESIGN

5.1. Overall Design

This study is a randomized, placebo-controlled, double-blind (sponsor unblind), parallel group, multi-center phase IIa trial in two equal sized cohorts (male or female). Following completion of screen assessments, baseline assessments will be conducted in eligible participants and, in each cohort, the participants will be randomized 1:1 to GSK2881078 or matching placebo.

Figure 1 Study Schematic

This study will assess the effect of GSK2881078 on physical strength and function after 13 weeks of treatment. The placebo group will serve as an appropriate control group in order to limit evaluation bias in the study endpoints. No suitable active comparator is currently available. Both treatment and control groups will be asked to participate in a standardized home exercise program. Study treatment will consist of two dosing cohorts (Male: placebo or 2.0 mg of GSK2881078; Postmenopausal female: placebo or 1.0 mg of GSK2881078). All participants will take their first dose of study treatment in the clinic following randomization, and will continue on a once daily dose for the duration of the treatment period. Participants will be dosed without regards to food intake. All doses should be administered in the clinic on study visit days during the treatment period. Time of dosing for the 2 doses prior to sample collection should be recorded and PK samples should be collected as specified in the SoA (Section 2).

The study will consist of a screening/baseline period of up to 30 days, a 13-week treatment period, and a 6-weeks post-treatment follow-up visit as described in the Time and Events table (Section 2). Unscheduled visits may be performed as needed to conduct optional assessments required to follow unresolved findings of clinical concern.

Participants will participate in a screening visit within 30 days prior to randomization and baseline assessments. Prior to randomization, eligible participants will need to have a functional muscle deficit as defined by the Short Physical Performance Battery (SPPB) inclusion criterion (Section 6.1). Eligible participants will also have physical activity and patient reported outcomes (PROs) recorded prior to baseline, and will need to

demonstrate compliance with completion of the electronic diaries and wearing the activity monitor prior to randomization.

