5.2. Number of Participants

At least 100 participants with COPD and muscle weakness will be randomized (25/arm) to target approximately 80 evaluable participants (20/arm). Men and women will be recruited into separate cohorts of at least 50 participants each, with each cohort containing a placebo and GSK2881078 arm. Sample size consideration and assumptions are discussed in more detail in Section 10.1.1 .

Within each cohort, equal numbers of male and female participants will be randomized in a 1:1 allocation using a central randomization system to receive one of the planned treatment regimens listed below:

Male participants: Placebo or 2.0 mg GSK2881078

Female participants: Placebo or 1.0 mg GSK2881078

Additional participants may be enrolled if the number of participants with exacerbations plus the number of participants withdrawn prematurely for other reasons is higher than anticipated (approximately 20%), or the precision of the estimates of the treatment effects based on the observed variability and treatment effect at an interim analysis. The total sample size may be increased by up to 60 participants (approximately 15/arm). Enrolment is not expected to exceed approximately 160 total participants.

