10.1.3. Sample Size Re-estimation or Adjustment

Based on the observed variability and treatment effects at an interim analysis, the sample size may be increased to improve the precision of the estimates of treatment effects and the operating characteristics of the end of study decision criteria. Strength, ISWT and ESWT will be considered in the sample size evaluation. Males and females will be evaluated separately. The sample size may be increased by up to 15 subjects/arm.

Details of the interim analysis will be described in the Reporting and Analysis Plan (RAP).

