10.3. Statistical Analyses

All analyses will be performed separately for females and males.

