
 
• The number of responders, odds ratio and associated 90% exact confidence intervals between treatment groups (GSK2881078 vs. placebo) will be reported for CAT and SGRQ responder analysis by gender.
 

Secondary Efficacy Endpoint / Variables – Single Post-baseline Visit

 
• Change and % change from baseline in Constant Work Rate (CWR) duration* from endurance shuttle walking test at Day 90.
 
• Change and % change from baseline in peak performance from incremental shuttle walking test at Day 90.
 
• Change from baseline in St George Respiratory Questionnaire (SGRQ) total score* and domain scores derived from SGRQ-c raw scores at Days 90.
 
 
*Bayesian analysis will be performed only for the endpoints change from baseline of Constant Work Rate (CWR) duration and change from baseline of SGRQ total score. The posterior probability of treatment difference greater than 36 seconds and less than 48 seconds for Constant Work Rate (CWR) duration and greater than 2 points and less than 4 points SGRQ total score will be estimated.

Model Specification

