
 
• Treatment difference (GSK2881078 – placebo) in the change from baseline and percentage change from baseline at Day 90 will be analysed using ANCOVA where baseline and treatment will be included as the independent variables in the model. Each gender will be analysed separately. The analyses will be based on the analysis population for the endpoints CWR duration, peak performance from incremental shuttle walking test and SGRQ total score additionally the endpoints CWR duration and SGRQ total score will be analysed for per-protocol population as well.
 
• If there are any departures from the distributional assumptions, the change of log-transformed data at post- baseline from log baseline will be the response variable, adjusted for treatment, and log-transformed baseline value.
 
• A Bayesian approach will also be conducted to estimate the treatment difference in the change from baseline at Day 90 for CWR duration and change from baseline SGRQ total score for the analysis population, following the similar procedures described in Section 7.1.4.1. for the primary efficacy endpoint analysis with the model being constructed as below:
 
• Create indicator variables for the categorical effect: Treatment (GSK2881078 vs. Placebo). For treatment, if treatment=placebo, then drug=0; if treatment=GSK2881078, then drug=1;
 
• For subject i on treatment j, the model can be written as:  <math display="block">CH_{ij} = \beta_0 + \beta_1 \text{ drug} + \beta_2 \text{ base} + \epsilon_{ij}</math>                     where CH refers to the change from baseline at Day 90; base means baseline assessment; drug=0 when treatment is placebo and drug=1 for GSK2881078 treatment; <math>\epsilon_{ij} \sim N(0, \sigma^2)</math>; <math>\beta_1</math> is the estimated treatment difference (GSK2881078 vs. placebo) at Day 90;
 
• Set seed=123456 with the simulation size of 200000 and 5000 burn-in iterations; the sample size and the number of burn-in iterations could be updated during the convergence check.
 
• The non-informative priors (normal (0, var=1e6)) will be used for the regression parameters <math>\beta_0</math>, <math>\beta_1</math>, and <math>\beta_2</math>. and the prior for variance <math>\sigma^2</math> will be the inverse gamma (0.01, scale=0.01)
 
• For calculating the posterior adjusted least square mean and corresponding difference, use the coefficient of L-matrix of the covariates from the corresponding ANCOVA analysis
 

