Note: The confidence interval for odds ratio (GSK2881078/Placebo) is calculated using the Exact method.

Programming note: continue for the next visit and repeat for Sex: Male.

for the treatment. In case of violation of the assumptions, the same model is fitted with log of ratio to baseline and replacing the covariate baseline with log baseline.

[2] GSK2881078-Placebo.

Example : EFF\_T8  
Protocol: XXXXXXXX  
Population: Analysis

Table XX  
Descriptive Summary of Patient Global Impression of Change

Sex: Female

Visit	Treatment	N	n	PGIC Category						
				Much Worse	Worse	Slightly Worse	No Change	Slightly Better	Better	Much Better
Day 14	GSK2881078	xx	xx	xx (xx.x%)	xx (xx.x%)	xx (xx.x%)	xx (xx.x%)	xx (xx.x%)	xx (xx.x%)	xx (xx.x%)
	Placebo	xx	xx	xx (xx.x%)	xx (xx.x%)	xx (xx.x%)	xx (xx.x%)	xx (xx.x%)	xx (xx.x%)	xx (xx.x%)
Day 28	GSK2881078	xx	xx	xx (xx.x%)	xx (xx.x%)	xx (xx.x%)	xx (xx.x%)	xx (xx.x%)	xx (xx.x%)	xx (xx.x%)
	Placebo	xx	xx	xx (xx.x%)	xx (xx.x%)	xx (xx.x%)	xx (xx.x%)	xx (xx.x%)	xx (xx.x%)	xx (xx.x%)
....										

Note: The percentages have been calculated based on n.

Programming note: Continue with Visit= Day 56, Day 90 and then repeat for Sex: Male

Example : EFF\_T9  
Protocol: XXXXXXXX  
Population: Analysis

Table XX  
Descriptive Summary of Patient Global Rating of Severity

Sex: Female  
Treatment: Placebo

Analysis Visit	N	n	PGRS Category				
			None	Mild	Moderate	Severe	Very Severe
Baseline	xx	xx	xx (xx.x%)	xx (xx.x%)	xx (xx.x%)	xx (xx.x%)	xx (xx.x%)
	xx	xx	xx (xx.x%)	xx (xx.x%)	xx (xx.x%)	xx (xx.x%)	xx (xx.x%)
Day 90	xx	xx	xx (xx.x%)	xx (xx.x%)	xx (xx.x%)	xx (xx.x%)	xx (xx.x%)
	xx	xx	xx (xx.x%)	xx (xx.x%)	xx (xx.x%)	xx (xx.x%)	xx (xx.x%)

....

Programming note: repeat for Sex: Male

Listings

Example : EFF\_L1  
 Protocol: XXXXXX  
 Population: Analysis

Listing XX  
 Listing of Leg Press Strength (kg) Results

Sex: Female  
 Treatment: XXXXX

Site Id/ Unique Subject Id	Visit / Analysis Visit	Assessment Date/Day	Parameter	Leg Press Performed? (if no, provide reason)	Assessment Value	Change/Percent Change from Baseline
	Unscheduled / Visit X Day	DDMMYY/1	Number of Successful Lifts	Yes	xx	xxxx / xxx.x
				No		
			Starting Lift Weight (Unit)	Yes	xx (xxx)	xxxx / xxx.x
			Last Successful Lift 1-RM (Unit)	No		

Note: Baseline value will be the latest pre-dose assessment with a non-missing value, including those from unscheduled visits.

Programming note: Sorted by treatment, Center, Subject, Visit and continue for SEX: Male  

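### The CAT and SGRQ responder comparisons carry no baseline covariate, although response is defined as a fall from baseline and the continuous CAT and SGRQ models adjust for it (minor)

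*SAP*

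**What the plan says.** **Responder comparison.** For CAT and SGRQ responders, the categorical block of SAP 7.2.4.1 plans "The number of responders, odds ratio and associated 90% exact confidence intervals between treatment groups", by sex. Unlike the blocks for continuous endpoints, it has no model specification row. Shell EFF_T6 shows responder counts and one odds ratio with its 90% interval, and adds "The confidence interval for odds ratio (GSK2881078/Placebo) is calculated using the Exact method". No footnote names a covariate, whereas shells EFF_T1 and EFF_T4 name baseline. The variant of exact method is not stated.

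**Definition of response.** SAP 12.6.2 defines a CAT responder by a fall in total score of at least 2 from baseline, and an SGRQ responder by a fall of at least 4.

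**Continuous analyses.** The SGRQ change at Day 90 "will be analysed using ANCOVA where baseline and treatment will be included as the independent variables in the model". The CAT change uses the same type of repeated-measures model as leg strength, which includes baseline. SAP 5.4.1 lists baseline as a general covariate, but nothing carries it into the responder tables.

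**Size.** Protocol 5.1 states that "in each cohort, the participants will be randomized 1:1 to GSK2881078 or matching placebo", and Protocol 10.3 that "All analyses will be performed separately for females and males". Protocol 5.2 says that at least 100 participants "will be randomized (25/arm) to target approximately 80 evaluable participants (20/arm"). Each responder table therefore compares about 20 with about 20.

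**The concern.** Whether a participant falls by a fixed amount depends on where that participant started. A very low scorer cannot fall by the threshold, and a high scorer tends to regress towards the mean. Baseline score therefore predicts response, and in arms of about 20 a chance imbalance in baseline moves the responder comparison. The SAP removes that component from the continuous CAT and SGRQ results but leaves it in the responder results for the same questionnaires, although the covariate is already collected. What is at stake is some precision in two secondary tables, and a reader's ability to set them beside the adjusted results.

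A second, smaller matter is the interval. An exact interval from a small two-by-two table usually covers more than its nominal level. The SAP does not say which exact method it means, nor that the limits are conservative relative to the model-based 90% intervals elsewhere.

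**Working it through.** **1. The plan's own figures.** The documents give no precision for the responder odds ratio. The figures they do give in Protocol 10.1.1 reproduce. For strength, t(0.95, 2n-2) x SD x sqrt(2/n) with SD 10.9 gives:
- n = 10: 1.734 x 10.9 x 0.4472 = 8.45 (stated 8.45)
- n = 20: 1.686 x 10.9 x 0.3162 = 5.81 (stated 5.8)

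With 20% dropout, 20/(1 - 0.2) = 25 per arm, as stated.

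**2. Gain from adjusting for baseline.** Assumed, because the documents give neither: test-retest correlation rho of 0.5 to 0.8, and change SD of 5 points for CAT. Mean change is taken as zero.

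- Correlation of baseline with change, in size: r = sqrt((1 - rho)/2), which is 0.500 at rho = 0.5 and 0.316 at rho = 0.8.
- Cut-off in SD units: z = 2/5 = 0.4. Response rate p = Phi(-0.4) = 0.345. SD of the response indicator: sqrt(0.345 x 0.655) = 0.475.
- Correlation of baseline with response: q = r x phi(z)/0.475 = r x 0.368/0.475 = r x 0.775, giving 0.387 and 0.245.
- Variance ratio, adjusted to unadjusted, allowing for the fitted covariate: (1 - q^2) x (1 + 1/(2n - 4)), with n = 20:
  - rho = 0.5: (1 - 0.150) x 1.028 = 0.87
  - rho = 0.8: (1 - 0.060) x 1.028 = 0.97

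Only threshold/SD enters, so the SGRQ cut-off of 4 with an assumed SD of 10 gives the same values. A rarer response gives less: at z = 0.8 and rho = 0.8, q = 0.316 x 0.709 = 0.224 and the ratio is 0.950 x 1.028 = 0.98. Simulation at both cut-offs gives a variance reduction of about 2-13%. In standard errors that is 1 - sqrt(0.98) = 1% to 1 - sqrt(0.87) = 7%.

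**3. What a chance imbalance does.** The unadjusted SE of the responder difference is 0.475 x sqrt(2/20) = 0.150, or 15 percentage points. A one-SE baseline imbalance shifts the difference by q x 0.150, which is 3.7 to 5.8 points and less than half an SE. This is the same effect as in step 2 seen from another side, not a further gain.

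**4. Which interval for the adjusted difference.** Response was simulated under the model of step 2 with 20 per arm, 8,000 trials per setting, and a linear model with treatment and baseline. Coverage of nominal 90% limits:

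| Limits | Coverage |
|---|---|
| Plain sandwich (HC0), normal quantile | 87-88% |
| HC3, t quantile | about 91% |
| Ordinary least squares, t quantile | about 90% |

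**5. Coverage of the exact interval.** All two-by-two tables were enumerated for two independent binomials, with 5% in each tail of the conditional distribution. Placebo response of 20-50% and odds ratios of 1 to 3 are assumed, because the documents give no rates.

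| Per arm | Exact, nominal 90% |
|---|---|
| 16 | 94.6-96.6% |
| 20 | 94.6-95.7% |
| 25 | 93.5-95.0% |
| 40 | 93.7-94.4% |

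At 20 per arm, mid-P limits cover 89.3-92.6%, and a minimum-likelihood exact interval covers 92.2-95.7%.

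Example, 12/20 against 6/20: the odds ratio is (12/8)/(6/14) = 3.5. Exact 90% limits are 0.97 to 12.7 and mid-P limits 1.12 to 10.7. The ratio of log widths is ln(12.7/0.97)/ln(10.7/1.12) = 2.57/2.26 = 1.14.

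**The case against.** **The unadjusted comparison is sound.** Under randomisation the odds ratio needs no covariate, and its interval already allows for chance imbalance. Baseline-adjusted results exist for both questionnaires on the continuous scale. This stands: the omission costs a little precision and is not a bias.

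**The gain is small and rests on assumptions.** The correlations and SDs are not in the documents, and the reduction is at most about 7% of a standard error. Adjustment would not make responder and continuous results agree either, because dichotomising alone can separate them. This also stands, and it limits the weight of the point.

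**Little depends on these tables.** Protocol section 10 assigned patient-reported outcomes to descriptive statistics. SAP Table 1 added the responder analyses to help the clinical team's review, and SAP 7.2.2 describes them as explored. Tables 2.18 and 2.22 are not among the headline results, EFF_T6 has no p-value, and the Bayesian SGRQ thresholds apply to the continuous score.

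**A stronger reading is tempting.** From coverage near 95%, a reader might infer that the 90% label is wrong, or that the method wastes participants. The documents do not support that. An exact 90% interval promises at least 90% and delivers it. Mid-P limits are narrower because they give up that guarantee, falling to 89.3% in the cases examined. The figure also depends on assumed response rates and on a tail-based method that the SAP does not name. Up to 15 more participants per arm were allowed ("The sample size may be increased by up to 15 subjects/arm"), and the excess is slightly smaller at that size.

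**Conclusion.** The point holds as a minor one. The responder comparisons leave out a covariate that the plan already collects and uses in the continuous models of the same questionnaires, and that bears directly on a response defined as a fall from baseline. Including it would cut the variance of the responder difference by about 2-13% at 20 per arm, given test-retest correlations of 0.5 to 0.8 and the assumed change SDs. The planned odds ratio remains valid.

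The interval deserves a clarification, not a correction. Read as tail-based and conditional, its 90% limits cover about 94-96% at 16 to 25 per arm for placebo response of 20-50%. They are conservative and correctly labelled. Neither matter touches the primary analysis or any decision rule.

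**What to change.** - **Main change.** In SAP 7.2.4.1 and EFF_T6, keep the odds ratio and state that it is unadjusted. Add to Tables 2.18 and 2.22 the responder difference (GSK2881078 minus placebo), by sex and visit, from a linear model with treatment and baseline CAT or SGRQ total score. Give a 90% CI with HC3 standard errors and t quantiles. The SAP must name the variance estimator and the quantile, because a plain sandwich interval would fall short of 90%.
- **Footnote.** Name the exact variant used. If it is tail-based, say that its limits are conservative at these sizes. Mid-P 90% limits may be shown beside it.

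The cost is a short model specification, one extra column in two tables, and a second effect scale for the reader. No new data are needed.

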8. DISCONTINUATION CRITERIA

8.1. Discontinuation of Study Treatment

A participant may discontinue treatment if they have a severe exacerbation of COPD requiring hospitalization or if they meet liver or QTc stopping criteria. A participant who discontinues study treatment should return to the clinic only for the follow-up visit within the specified window if possible. Only the safety assessments for the follow-up visit (physical examination, 12-lead ECG, vitals, blood tests, urinalysis and concomitant medication review) should be conducted in these participants as described in the SoA and Section 9.4.

[figure not shown]

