9.2.4.2. St George Respiratory Questionnaire COPD (SGRQ-c)

The SGRQ-c (http://www.healthstatus.sgul.ac.uk/SGRQ_download/sgrq-c-manual-april-2012.pdf) has been developed using COPD data only to measure general health related quality of life, and is a validated questionnaire for COPD. It consists of 40 items in total, corresponding to 3 individual domains: symptoms, activity and impact, with different components carrying a different weighting. The score range is from 0 (no impairment) to a theoretical maximum of 3201.9 for the worst possible state of the participant. The

minimal clinically important difference for a change in SGRQ-c is 4.0 points [Jones , 2005]. The SGRQ-c will be completed at baseline and day 90.

9.2.4.3. Patient Global Rating of Severity (PGRS) and Patient Global Impression of Change (PGIC)

The PGRS is a single global question that asks participants to rate how their condition impacts their ability to perform physical activity on a five-point scale (none, mildly, moderately, severely, very severely).

Responses to the PGIC question will be on a 7 point Likert scale ranging from much better to much worse.

The PGRS will be completed only at baseline and day 90. However, the PGIC will be completed at day 14, 28, 56, 90 and at the follow up visit.

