### 5.2. Baseline Definitions

Parameter	Study Assessments Considered as Baseline			Baseline Used in Data Display
	Screening	Day -9	Day 1 (Pre-Dose)	
Efficacy				
Leg Strength	X		X	whichever is latest*
Incremental Shuttle Walk Test		X	X	whichever is higher
Endurance Shuttle Walk Test			X	Day 1
Dual-energy X-ray Absorptiometry (DXA)			X	Day 1
Short Physical Performance Battery (SPPB)	X		X	whichever is latest*
COPD Assessment Test (CAT)			X	Day 1
Patient Global Rating of Severity (PGRS)			X	Day 1
St George Respiratory			X	Day 1

Parameter	Study Assessments Considered as Baseline			Baseline Used in Data Display
	Screening	Day -9	Day 1 (Pre-Dose)	
Questionnaire COPD (SGRQ-c)				
PROactive Physical Activity	X	X		See detail below**
Spirometry	X		X	whichever is latest*
Sniff Nasal Inspiratory Pressure (SnIP)	X		X	whichever is latest*
Safety				
Vital Signs	X		X	whichever is latest*
12-lead ECG	X		X	whichever is latest*
Haematology	X		X	whichever is latest*
Clinical Chemistry	X		X	whichever is latest*
Urinalysis	X		X	whichever is latest*
hsCRP, Fibrinogen			X	Day 1
Lipid panel	X		X	whichever is latest*
PSA	X		X	whichever is latest*
HbA1c	X			screening
Exploratory				
Cardiac and liver MRI			X	Day 1
Handgrip strength	X		X	whichever is latest*
Reproductive Tissue Biomarkers			X	Day 1
Bone Biomarkers			X	Day 1
***Exploratory Biomarkers			X	Day 1
***Monitored home exercise program		X	X	whichever is latest*

\*Baseline value will be the latest pre-dose assessment with a non-missing value, including those from unscheduled visits. If time is not collected, Day 1 assessments are assumed to be taken prior to first dose and used as baseline.

\*\*Baseline will be the average of the data collected from the 7-day period after Day -9 device dispense.

\*\*\*Exploratory Biomarkers and home exercise program will be analysed separately and will not be reported as part of this study Statistical Analysis Complete reporting.

Unless otherwise stated, if baseline data is missing no derivation will be performed and baseline will be set to missing.

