### 7.2.2. Summary Measure

The adjusted mean treatment differences (GSK2881078 – Placebo) for the following endpoints will be presented:

- Change and % change from baseline in appendicular, and total lean mass as assessed by Dual-energy X-ray Absorptiometry (DXA) at Days 28, 56 and 90.
- Change from baseline in total Short Physical Performance Battery (SPPB) score, times for chair rise and 4 m gait speed at Days 28, 56 and 90.
- Change and % change from baseline in Constant Work Rate (CWR) duration from endurance shuttle walking test at Day 90.
- Change and % change from baseline in peak performance from incremental shuttle walking test at Day 90.
- Change from baseline in PROactive endpoints at Days 56 and 90. (individual components and total score).
- Change from baseline in COPD Assessment Test (CAT) score at Days 56 and 90.
- Change from baseline in St George Respiratory Questionnaire (SGRQ) total score and domain scores derived from SGRQ-c raw scores at Days 90.

The responder analysis between GSK2881078 and Placebo (GSK2881078/ Placebo) for the following endpoints will be explored

- Odds ratio between treatment groups for the COPD Assessment Test (CAT) responder at Days 56 and 90.
- Odds ratio between treatment groups for the St George Respiratory Questionnaire (SGRQ) responder defined by the total score derived from SGRQ-c raw scores at Days 90.

The descriptive summaries will be reported for the following endpoints

- Change from baseline in forced expiratory volume in 1 second (FEV1).

- Frequency and percentages of Patient Global Impression of Change (PGIC) responses.
- Frequency and percentages of Patient Global Rating of Severity (PGRS) responses.
- Change from baseline in Sniff nasal inspiratory pressure (SnIP).
- Change in physical activity measures as assessed via an accelerometer.

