**Summary Results Presentation**

Baseline, each postbaseline visit and change from baseline, will be descriptively summarized by treatment group for endpoints: weekly average steps, vector magnitude unit/wear time and moderate/vigorous activity duration measures via an accelerometer. The number of subjects with the eligible days i.e. wear duration more than 8 hours for at least 4 days, the average eligible days for those subjects and average wear duration (minutes) during the eligible days will be summarized.

Baseline, each postbaseline visit and change from baseline, will be descriptively summarized by treatment group for original FEV1 (L) and percentage predicted FEV1 and maximum SnIP.

In addition, a box plot will be prepared for the change from baseline for FEV1 and SnIP at the post-baseline visits.

For the categorical endpoints, PGRS and PGIC, the count and percentage will be summarized by category and treatment for each visit separately by gender.

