**CONFIDENTIAL**

200182

Safety					
45.	Safety	SAFE_L1	Listing of COPD Exacerbation Log		SAC
46.	Safety	SAFE_L2	Listing of Hepatic, Prostate and Cardiac Structure assessed via MRI		SAC
47.	Safety	SAFE_L3	Listing of Change from baseline of Lipids and Sex hormones	List the sex hormones Testosterone, Free Testosterone, Sex hormone-binding globulin (SHBG), Follicle-stimulating hormone (FSH), Luteinizing hormone (LH) and Prostate specific antigen (PSA).	SAC
Primary Efficacy					
48.	Analysis	EFF_L1	Listing of leg Press Strength (kg) Results		SAC
Secondary Efficacy					
49.	Analysis	EFF_L2	Listing of Appendicular (kg), and Total Lean Mass (kg) as Assessed by Dual-energy X-ray Absorptiometry (DXA)		SAC
50.	Analysis	EFF_L3	Listing of PROactive Endpoints	Total score, difficulty and amount scores will be displayed	SAC
51.	Analysis	EFF_L4	Listing of Total Short Physical Performance Battery (SPPB) Score and Times for Chair Rise (sec) and 4 m Gait Speed (sec) Results		SAC
52.	Analysis	EFF_L5	Listing of Constant Work Rate (CWR) Duration (sec) from Endurance Shuttle Walking Test		SAC
53.	Analysis	EFF_L6	Listing of Peak Performance from Incremental Shuttle Walking Test		SAC
54.	Analysis	EFF_L7	Listing of COPD Assessment Test (CAT)		SAC
55.	Analysis	EFF_L8	Listing of Patient Global Impression of Change		SAC
56.	Analysis	EFF_L9	Listing of Patient Global Rating of Severity		SAC

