Note: When there are multiple pre-dose assessments, the highest non-missing pre-dose assessment from day -9 and day 1 is identified and captured as "Baseline (Derived)" visit.

Programming note: Sorted by treatment, Center, Subject, Visit and continue for SEX: Male

Programming note: Use assessment datetime instead of date if time collected and update the label as "Assessment Datetime/Day"

Example : EFF\_L7  
Protocol: XXXXXXXX  
Population: Analysis

Page 1 of 1

Listing xx  
Listing of COPD Assessment Test (CAT)

Sex: Female  
Treatment: XXXXXX

Site Id/ Unique Subject Id	Visit / Analysis Visit	Assesment Date/Day	Individual Question Score								Total Score/Chang from Baseline
			1	2	3	4	5	6	7	8	
xxxxxx/ xxxxxx	Xx	DDMMYYYY	Xx	xx	xx	xx	xx	xx	xx	xx	xx
xxxxxx/ xxxxxx	Unscheduled / Day xx	DDMMYYYY									

CONFIDENTIAL

200182

Note: 1="Frequency of Cough", 2="Amount of Phlegm in My Chest", 3="Tightness in Chest", 4="Breathless Walking Upstairs", 5="Limited Doing Home Activities", 6="Confident Leaving Home", 7="Sleeping Soundly", 8="Amount of Energy".

Note: "Visit 3, Day 1" is considered as Baseline.

Programming note: Sorted by treatment, Center, Subjects, Visit and continue for SEX: Male

Programming note: Use assessment datetime instead of date if time collected and update the label as "Assessment Datetime/Day"

Example : EFF\_L8  
Protocol: XXXXXX  
Population: Analysis

Page 1 of x

Listing xx  
Listing of Patient Global Impression of Change

Sex: Female  
Treatment: XXXXXX

Site Id/Unique Subject Id	Assessment Date/Day	Visit / Analysis Visit	PGIC Category						
			Much Worse	Worse	Slightly Worse	No Change	Slightly Better	Better	Much Better
	DDMMYYYY /14	Visit x / Visit X Day X	No	No	No	No	Yes	No	No
	DDMMYYYY/1	xx							

Programming note: Sorted by treatment, Center,Subjects, Visit and continue for SEX: Male

Programming note: Use assessment datetime instead of date if time collected and update the label as "Assessment Datetime/Day"

Example : EFF\_L9  
Protocol: XXXXXXXX  
Population: Analysis

Page 1 of x

Listing xx  
Listing of Patient Global Rating of Severity (PGRS)

Sex: Female  
Treatment: XXXXX

Site Id/ Unique Subject Id	Assessment Date/Day	Visit / Analysis Visit	PGRS Category				
			None	Mild	Moderate	Severe	Very Severe
Xxxx/xxxx		Baseline / Visit X Day X					Yes

....

Programming note: Sorted by treatment, Center, Subjects, Visit and continue for SEX: Male  

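### No planned table or figure summarises within-person change in PGRS; Table 2.42 gives only separate category counts at Baseline and at Day 90

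*SAP*

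**What the plan says.** Protocol 4 and SAP 2.2 list PGRS as a secondary endpoint under the objective on the effect of about 13 weeks of dosing. It has five levels, from none to very severe. On timing, Protocol 9.2.4.3 states: "The PGRS will be completed only at baseline and day 90".

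SAP 7.2.2 sets the summary measure as "Frequency and percentages of Patient Global Rating of Severity (PGRS) responses". SAP 7.2.4.1 adds: "For the categorical endpoints, PGRS and PGIC, the count and percentage will be summarized by category and treatment for each visit separately by gender".

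The table is 2.42, "Descriptive Summary of Patient Global Rating of Severity", in the Analysis Population. The shell with that title in SAP Appendix 12 is labelled EFF_T9, although the list of displays points Table 2.42 to EFF_T10. EFF_T9 shows Baseline and Day 90 rows, each with N, n and the five categories. It has no shift, change or paired block. SAP 12.11.6 plans no PGRS figure, and SAP 7.2.3 does not include PGRS in the Per Protocol analyses.

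The SAP also plans Listing 56, "Listing of Patient Global Rating of Severity" (shell EFF_L9), which gives each participant's category by visit, sorted by treatment, centre, subject and visit.

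On early stopping, Protocol 8.1 says: "A participant who discontinues study treatment should return to the clinic only for the follow-up visit within the specified window if possible". Only safety assessments are done at that visit, and Protocol 10.2 rules out imputation.

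**The concern.** One PGRS rating describes present severity. Unlike the Patient Global Impression of Change (PGIC), it carries no information on change, so the effect of 13 weeks of dosing shows only when two ratings from the same person are compared. Table 2.42 leaves that comparison out. The SAP prints change-from-baseline blocks for its continuous endpoints (shell EFF_T3) and plans shift tables for laboratory data (shell LB4), so the format is already in use.

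Two things follow. Equal category percentages at both visits could hide many individual changes. And if those without a Day 90 rating differ in severity from the rest, the Day 90 row will look better or worse than Baseline because of who is missing from it. A severe or steroid-treated COPD exacerbation leads to permanent discontinuation of treatment (Protocol 8.2), so a link between loss and severity is plausible, though the documents do not show one.

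**Working it through.** **Inputs from the documents.** Protocol 5.2 plans 25 randomised and about 20 evaluable per arm within each sex, with about 20% expected to have an exacerbation or withdraw early. These agree: 20 / (1 − 0.20) = 25.

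**Assumptions.** The documents give no baseline PGRS distribution. I assume 12 of 25 (48%) rated severe or very severe, 5 leavers who have all entered the Analysis Population, and no change in anyone's rating.

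**Effect of loss alone.** If s of the 5 leavers were severe or worse, the Day 90 share is (12 − s) / 20.

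| s | Day 90 share | Apparent shift from 48% |
|---|---|---|
| 0 | 12/20 = 60% | +12 points |
| 4 | 8/20 = 40% | −8 points |
| 5 | 7/20 = 35% | −13 points |

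**Sensitivity.** For other assumed baseline shares, from 20% to 80% of 25, the extreme shifts are:

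- 5 leavers: −20 points (5/25 = 20% becomes 0/20) to +20 points (20/25 = 80% becomes 20/20).
- 2 leavers: −7.0 points (5/25 = 20% becomes 3/23 = 13.0%) to +7.0 points (20/25 = 80% becomes 20/23 = 87.0%).
- 1 leaver: −3.3 points (5/25 = 20% becomes 4/24 = 16.7%) to +3.3 points (20/25 = 80% becomes 20/24 = 83.3%).

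**Information lost even without dropout.** Take 20 people with both ratings, 10 severe and 10 moderate at each visit. The two rows are identical if nobody changed. They are also identical if all 10 severe became moderate and all 10 moderate became severe. So the same printed table fits anything from 0 to 20 people changing category.

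**After pairing.** If the same people are counted at both visits, the row-to-row shift caused by loss is 0 by construction. If nobody changed, every off-diagonal cell of the shift table is 0.

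**The case against.** The strongest defence is that the table matches the endpoint as specified. PGRS is listed by name, without the change-from-baseline wording used for the continuous endpoints. Protocol 10 plans descriptive statistics for patient-reported outcomes, no test or threshold applies to PGRS, and SAP 7.2.3 does not name it among the decision-making endpoints. PGIC is tabulated by arm and sex through Day 90 and gives a patient-rated view of change. All of this stands, and it limits the importance of the point.

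The randomised arms can also be compared directly at Day 90. That is fair, but in a small trial such a comparison takes in chance baseline imbalance. At a 48% share with 25 per arm, the standard error of a baseline difference between arms is √(2 × 0.48 × 0.52 / 25) = 0.141, about 14 points.

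A reader might infer more than the documents support:

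- *That no output shows whether anyone's rating changed.* Listing 56 shows each participant's category by visit. It has no change column and is not tabulated by arm, but the information is there.
- *That the defined baseline goes unused, or that the rows describe different people.* Baseline is a row of EFF_T9. Both rows use the Analysis Population, the Day 90 set is essentially a subset of the Baseline set, and n is printed on each row. The printed n shows how many are missing but not which categories they came from.
- *That loss will produce a false treatment effect.* With 3 leavers in one arm and 7 in the other, all severe, Day 90 would show 9/22 = 40.9% against 5/18 = 27.8%, a gap of about 13 points. That split is a worst case with no source in the documents, which give no direction for the loss.

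**Conclusion.** The point holds as a minor gap in presentation: within-person PGRS change is collected and listed but not summarised in any planned table or figure. The 35% to 60% range rests on an assumed 48% baseline share and on 5 leavers per arm.

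Five is probably too many. The planned 20% counts participants with exacerbations as well as early withdrawals, and Protocol 8.2 requires stopping only for severe or oral-steroid-treated exacerbations, so 20% is not the rate of missing Day 90 ratings. Analysis Population membership needs a post-baseline lean mass, PROactive or functional assessment (SAP 4). The first is scheduled at Day 28, so people who leave before then are generally in neither row. Fewer leavers mean a smaller shift. That the two sets of counts cannot show individual change does not depend on any loss.

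**What to change.** Add to Table 2.42, by arm and sex:

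1. a Baseline-by-Day 90 shift table in participants with both ratings;
2. the number and percentage improved by at least one category, unchanged, and worsened;
3. the baseline distribution of participants without a Day 90 rating.

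Correct the shell reference in the same edit (Table 2.42 cites EFF_T10; the PGRS shell is labelled EFF_T9). Add the note, present in EFF_T8 but absent from EFF_T9, that percentages are based on n.

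The cost is one reprogrammed descriptive table from data already collected. The shift table will be sparse at about 20 per arm, so the improved, unchanged and worsened counts will be the readable part. It also remains a completers-only summary: it removes the row-to-row composition artefact but not possible selective dropout between arms. Item 3 lets a reader judge that.
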